### **7.2. Derived and transformed data**

#### **7.2.1. Date derivation**

- SAS date derived from a character date: In case day is missing, 15 is used. In case day & month are missing, 30 June is used.

### 7.2.2. Demography

- The continuous variable age [years] at the Persistence visit will be computed as the difference between the informed consent date and the date of birth /365.25.
- The continuous variable age [months] at the time of first or second dose of *Havrix* is computed based on the number of days between the administration of *Havrix* and the date of birth /30.5.
- The time interval [months] between first and second dose of *Havrix* is derived as the difference between date on second dose and date of first dose plus 1 day /30.5.
- Time interval [years] between last *Havrix* vaccination dose and the Persistence visit will be derived using the date of the visit minus the date of the last *Havrix* vaccination plus 1 day / 365.25.

### 7.2.3. Antibody persistence

- For a given subject and given antibody concentrations, missing or non-evaluable measurements will not be replaced. Therefore, we will exclude these subjects with missing or non-evaluable measurements.
- The Geometric Mean Concentrations (GMCs) calculations will be performed by taking the anti-log of the mean of the log concentrations transformations. Antibody concentrations below the cut-off (15 mIU/mL) of the assay will be given an arbitrary value of half the cut-off of the assay for the purpose of GMC calculation.
- A seronegative subject is a subject whose antibody concentration is below the cut-off value of the assay. A seropositive subject is a subject whose antibody concentration is greater than or equal to the cut-off value of the assay.
- The assay cut-off is the value under which there is no quantifiable result available. For an assay with a specific ‘cut\_off’, numerical immuno result is derived from a character field (rawres):
  - If rawres is ‘NEG’ or ‘-’ or ‘(-)’, numeric result= cutt\_off/2,
  - if rawres is ‘POS’ or ‘+’ or ‘(+)’, numeric result = cut\_off,
  - if rawres is ‘< value’ and value<=cut\_off, numeric result =cut\_off/2,
  - if rawres is ‘< value’ and value>cut\_off, numeric result =value,
  - if rawres is ‘> value’ and value<cut\_off, numeric result =cut\_off/2,
  - if rawres is ‘> value’ and value>=cut\_off, numeric result =value,
  - if rawres is ‘<= value’ or ‘>= value’ and value<cut\_off, numeric result =cut\_off/2,
  - if rawres is ‘<= value’ or ‘>= value’ and value>=cut\_off, numeric result =value,

- if rawres is a value < cut\_off, numeric result = cut\_off/2,
- if rawres is a value >= cut\_off, numeric result = value,
- else numeric result is left blank.

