6.6.3. Laboratory assays

Please refer to [APPENDIX A](#) for a detailed description of the assays performed in the study. Please refer to [APPENDIX B](#) for the address of the clinical laboratories used for sample analysis.

Serological assays for the determination of antibodies against HAV will be performed by ELISA using standardised and validated procedures at GSK Biologicals' laboratory or in a laboratory designated by GSK Biologicals. Subjects will be defined as being seropositive if their anti-HAV antibody concentration is ≥ 15 mIU/mL

Table 5 Humoral immunity (antibody determination)

System	Component	Method	Kit / Manufacturer	Cut-off	Unit	Laboratory*
SER	Hepatitis A Virus Antibodies	ELI	Enzygnost (Siemens Healthcare)	15	mIU/mL	GSK Biologicals**

SER = Serum

ELI = Enzyme-linked immunosorbent assay

*Refer to [APPENDIX B](#) for the laboratory addresses.

**GSK Biologicals laboratory refers to the Clinical Laboratories Sciences (CLS) in Rixensart, Belgium; Wavre, Belgium

The GSK Biologicals' clinical laboratories have established a Quality System supported by procedures. The activities of GSK Biologicals' clinical laboratories are audited regularly for quality assessment by an internal (sponsor-dependent) but laboratory-independent Quality Department.

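### SAP 7.2.3 scores some bounded assay results as seropositive (`<30`, `<=15`) although the bound does not show a concentration of 15 mIU/mL or more; minor, and relevant only if such strings occur

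*SAP*

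**What the plan says.** Protocol 6.6.3 sets the rule for the primary endpoint: "Subjects will be defined as being seropositive if their anti-HAV antibody concentration is ≥ 15 mIU/mL". SAP 7.2.3 repeats the definition and gives half the cut-off (7.5) to concentrations below 15. It then lists how the character field is converted. The lines that matter here are:

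- `<` at or below the cut-off: "if rawres is ‘< value’ and value<=cut\_off, numeric result =cut\_off/2"
- `<` above the cut-off: "if rawres is ‘< value’ and value>cut\_off, numeric result =value"
- `>` below the cut-off: "if rawres is ‘> value’ and value<cut\_off, numeric result =cut\_off/2"
- `<=` or `>=` below the cut-off: "if rawres is ‘<= value’ or ‘>= value’ and value<cut\_off, numeric result =cut\_off/2"
- `<=` or `>=` at or above the cut-off: "if rawres is ‘<= value’ or ‘>= value’ and value>=cut\_off, numeric result =value"

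Strings that match no line fall to the last one: "else numeric result is left blank". On missing or non-evaluable measurements the section says: "Therefore, we will exclude these subjects with missing or non-evaluable measurements". It also explains that the cut-off is the level below which the assay yields no quantifiable result.

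**The concern.** A bound is informative about serostatus only if every value it allows lies on one side of 15. `<30` allows values on both sides, and so does `<=15`, because 15 itself is seropositive and anything lower is not. The list nevertheless gives both a number at or above the cut-off, and so a positive status. This conflicts with the definition in the same section. One line also handles `<=` and `>=` alike, although they bound in opposite directions.

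The derived number feeds the primary endpoint (SAP 4.1), the GMCs and GMC ratio, and the comparison with the -10% limit (SAP 6.2). The blank branch does not catch these strings, because each one matches an explicit line. The SAP's planned sensitivity analyses concern exclusions from the ATP cohort above 5% (SAP 6.2) and suspected natural infection (SAP 9), not ambiguous bounds.

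**Working it through.** **Inputs.** Cut-off 15 mIU/mL (Protocol 6.6.3, SAP 7.2.3). 260 evaluable subjects per group, 80% seropositive in both groups, limit -10%, one-sided alpha 2.5%, stated power 80.9% (Protocol 8.2, Table 10). No document gives a frequency for bounded strings.

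**Planning figure reproduced.** The restricted rates at a difference of -0.10 are 0.7411 and 0.8411.

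- SE0 = sqrt((0.7411×0.2589 + 0.8411×0.1589)/260) = 0.0354
- SE1 = sqrt(2×0.8×0.2/260) = 0.0351
- Power = Φ((0.10 − 1.96×SE0)/SE1) = 80.9%, as in Table 10. It is not in dispute; it fixes the planning case of 208/260 per group.

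**Rules applied to example strings.**

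| String | SAP value | Scored | What the bound implies |
|---|---|---|---|
| `<15` | 7.5 | negative | negative |
| `<30` | 30 | positive | undetermined |
| `<=15` | 15 | positive | undetermined |
| `>10` | 7.5 | negative | undetermined |
| `>=10` | 7.5 | negative | undetermined |
| `>15`, `>=15` | 15 | positive | positive |

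The ordinary below-cut-off string `<15` is handled correctly. The `<=15` row applies the numeric condition to both operators, which is the natural reading of a line without brackets.

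**Effect of one result at n = 260.**

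- Rate: 1/260 = 0.38 points.
- GMC, `<30` entered as 30 instead of 7.5: (30/7.5)^(1/260) = 4^(1/260) = 1.0053, about +0.5%.
- GMC, `<=15` entered as 15 instead of 7.5: 2^(1/260) = 1.0027, about +0.3%.
- GMC, `>10` entered as 7.5: no effect if the true value is below 15, because the SAP enters such a value as 7.5 anyway. If the true value is 15 or more, the factor is at most 2^(-1/260) = 0.9973, a fall of at least about 0.3%.

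**Lower 95% limit of the difference, 1-dose minus 2-dose (percentage points).** I assume a Miettinen-Nurminen score interval for what SAP 7.1 calls method 6.

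| 1-dose | 2-dose | Lower limit | Criterion |
|---|---|---|---|
| 208/260 | 208/260 | -6.91 | met |
| 207/260 (one scored negative) | 208/260 | -7.32 | met |
| 207/259 (one blank) | 208/260 | -7.00 | met |
| 201/260 | 208/260 | -9.76 | met |
| 200/260 (one scored negative) | 208/260 | -10.17 | not met |
| 200/259 (one blank) | 208/260 | -9.86 | met |
| 200/260 | 207/260 (one scored negative in each group) | -9.80 | met |

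From the planning case, seven rescored 1-dose results give 201/260 and still meet the criterion; the eighth gives 200/260 and fails it.

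The crossing does not depend on the choice of interval. The Wald limits are:

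- 201/260: -2.69 − 1.96×sqrt((0.7731×0.2269 + 0.8×0.2)/260)×100 = -9.73
- 200/260: -3.08 − 1.96×sqrt((0.7692×0.2308 + 0.8×0.2)/260)×100 = -10.14

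**The case against.** The strongest objection is that the strings may never occur. The list is generic: it is worded for any assay with a cut-off and also covers plain POS and NEG entries. The study has one assay with one cut-off, and the assay's performance is in an internal validation document (Protocol Appendix A) that is not included. This stands, and it keeps the point minor. It does not make the lines correct, because the SAP states them as the rule for this study's primary endpoint.

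The lower-bound half is weaker still. If nothing below 15 is quantifiable, a string such as `>10` should hardly arise. Nor is it a fault in itself that 7.5 lies outside what `>10` allows: a plain result of 12 also becomes 7.5, which is how half-cut-off substitution works. Only the serostatus of `>10` is open to question.

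The `<=15` example depends on punctuation. If the numeric condition attached only to `>=`, every `<=` string would match both combined lines, and the first would give 7.5. That reading makes the two lines conflict, so it is unlikely to be meant, but the wording leaves it open. `<30` does not depend on this.

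An indeterminate result might also be removed before the derivation. The SAP states no order between exclusion and derivation, and the elimination criteria are in a separate form that is not included. The list as written, however, gives these strings a value.

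Finally, the single-result reversal needs a chosen borderline case, and the protocol regards the comparison as exploratory, allowing no conclusions (Protocol 8.7). Both are true.

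**Conclusion.** The rule is wrong as written, and the point is minor. An upper bound of `<` above 15, or `<=` at or above 15 on the natural reading, is scored seropositive without evidence of 15 mIU/mL or more. Secondarily, `>` or `>=` with a bound below 15 is scored seronegative without being settled.

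The size is 0.38 points per misclassified child at 260 per group, with GMC shifts of about 0.3% to 0.5% for the upper-bound examples. The -10% criterion is safe against a single result at the planning rates and open to one only near the limit. If no such string occurs, nothing changes. The figures rest on the protocol's 260 per group and 80% rates, and on the assumed score interval.

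A reader might infer that the study's seropositivity rates are inflated, or that the rule tilts the comparison toward the 1-dose schedule. The documents support neither. They show no occurrence of these strings and give no reason why they would cluster in one dose group, and the lower-bound lines err in the opposite direction.

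**What to change.** In SAP 7.2.3:

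1. Give `<=` and `>=` separate lines.
2. State that a bounded result that does not settle status relative to 15 mIU/mL (`<` above 15, `<=` at or above 15, `>` or `>=` below 15) is non-evaluable and left blank.
3. Report the count of such results per dose group and epoch.
4. Only if the count is above zero, repeat the seropositivity difference once with these results scored least favourably: 1-dose seronegative, 2-dose seropositive. This is needed because blanking can itself favour seropositivity, as the 200/259 row shows.

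The other conversion rules stay as they are. The cost is a few lines of derivation code and one or two sentences in the SAP. The downside is possibly a few more non-evaluable subjects; the documents give no basis for a number.

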### 7.3. Number of decimals

The following decimal description will be used for the demography and persistence tables.

Display Table	Parameters	Number of decimal digits
Demographic characteristics	Mean, median age	1
Demographic characteristics	SD (age)	1
Persistence	Ratio of GMC	2
Persistence	Mean, Min, Q1, Median, Q3, Max for GMC	1
All summaries	% of count, including LL & UL of CI	1
All summaries	% of difference, including LL & UL of CI	2

## 8. CONDUCT OF ANALYSES

### 8.1. Sequence of analyses

Description	Analysis ID	Disclosure Purpose	Reference for TFL
Analysis of epoch 1 (Year 8)	E1_02	CTRS	All tables from TFL dated 29Jan2018
Analysis of epoch 2 (Year 10)	E1_01	Study report	All tables from TFL dated 29Jan2018

### 8.2. Statistical considerations for interim analyses

No interim analysis is planned. However the analysis will be done separately for the two epochs. As all analyses are descriptive, no adjustment of type I error is needed.

## 9. CHANGES FROM PLANNED ANALYSES

The histogram of anti-HAV log titer will be used to explore the possible outliers (subjects with very high concentrations that may have been elicited by natural HAV infection) in the study and if we detect a suspicious situation of natural infection we will do an additional analysis which determines a ‘natural infection cut-off’ by using the method described in the publication reference [[Wiedermann, 2007](#)] or a more appropriate method. We will perform a sensitivity analysis by excluding the potential outliers detected with the ‘natural infection cut-off’.

